4.5.3 Additional safety assessments

4.5.3.1 Clinical laboratory evaluations

Laboratory values, including markedly abnormal laboratory values will be presented descriptively by treatment group for the SS.

Tables presenting markedly abnormal values and those based on CTCAE grade (see section 6.13) will only include selected laboratory variables.

For tables where data are summarized by visit, unscheduled and repeat visits will not be summarized, but these data will be included in listings. Assessments collected at SFU visit should be included in by-visit tables. For tables where multiple measurements over a period of time are considered (as in shift tables), unscheduled and repeat visits will be considered as long

as they were collected in the period being summarized. All summaries will be presented in SI units and will be based on observed case values. In the case where laboratory values are below the lower limit of quantification, then these will be set to the midpoint between 0 and the lower limit of quantification for the purpose of summarizing the data. Only central laboratory results will be used in table analysis, while local laboratory results will only be displayed in listings.

For summaries for the ITP and Initial and Maintenance Period (combined) where multiple measurements across different visits are considered (as of markedly abnormal values tables, minimum/maximum post-baseline CTCAE tables, and shift tables), the laboratory results will be attributed according to their sampling date and time at risk for each period (see Section 4.5.1).

The following analyses will be presented:

- A summary of the absolute and change from Baseline values in each laboratory variable by treatment group and visit for the SS displaying the Placebo/BKZ 320mg Q4W and BKZ 320mg Q4W/Q8W.
- A summary of the number and percentage of study participants experiencing markedly abnormal values at any time while on treatment (ie, assessment on or following the first dose of IMP through the last dose of IMP + 119 days, occurring at scheduled and unscheduled visits) by laboratory variable and treatment group. Baseline values and values observed more than 119 days after the last administration of IMP are not considered. Two separate tables will show results for the ITP (for the SS) and the initial and maintenance treatment period (combined) (for the AMS). See section 6.10.1 for the criteria for markedly abnormal values.
- A summary of the number and percentage of study participants with a given CTCAE grade (0,1,2,3, or 4) based on minimum/maximum post-baseline value by laboratory variable and treatment group. Two separate tables will show results for the ITP (for the SS) and the initial and maintenance treatment period (combined) (for the AMS).
- Shift tables of the number and percentage of study participants experiencing CTCAE grade 0,1,2,3, or 4 values (as applicable) at Baseline to minimum/maximum post-Baseline CTCAE grade, by laboratory variable and treatment group. Two separate tables will show results for the ITP (for the SS) and the initial and maintenance treatment period (combined) (for the AMS).
- By-study participant listings of all laboratory data (including urinalysis) will be provided. These listings will be presented by treatment group and will include: center, study participant identifier, age, sex, race, weight, visit, laboratory variable, result (with abnormal values flagged as “L” or “H” accordingly) and unit.
- A separate listing will be provided for laboratory results classified as Grade 3 or Grade 4 for the SS.

The table for markedly abnormal liver function tests (LFTs) will contain data beyond the CTCAE Grade 3 thresholds outlined in Section 6.10.1 in order to allow for a more thorough review of elevated LFTs. There will be one table which will list the count and percentage of study participants meeting the below criteria at any time during the study:

- AST: >3xUpper Limit of Normal (ULN), >5xULN, >8xULN, >10xULN, >20xULN
- ALT: >3xULN, >5xULN, >8xULN, >10xULN, >20xULN

- AST or ALT: >3xULN, >5xULN, >8xULN, >10xULN, >20xULN
- Bilirubin: >1.5xULN, >2xULN
- ALP: >1.5xULN

For any participant with at least one markedly abnormal LFT (AST >3xULN, ALT >3xULN, bilirubin >3xULN, or ALP >1.5xULN) the New Ratio (nR) will be calculated as the ratio of either maximum ALT or maximum AST (whichever is higher) to ALP, all expressed as multiples of their ULN as follows:

- $nR = [\text{maximum}(\text{ALT/ULN or AST/ULN})]/(\text{ALP/ULN})$

A plot displaying shift in liver function tests from baseline to maximum post-baseline result and a plot showing maximum post-baseline Total Bilirubin versus maximum post-baseline AST and ALT will be provided for the AMS if there are study participants with reported markedly abnormal LFT.

The following definition of potential drug induced liver injuries (pDILI) will be used (all criteria must be met at the same assessment):

- (AST or ALT \geq 3xULN) and Total Bilirubin \geq 1.5xULN
- (AST or ALT \geq 3xULN) and Total Bilirubin \geq 2xULN

A table for pDILI will be presented by treatment group for study participants with at least one post-Baseline liver laboratory assessment. Number and percentage of study participants meeting laboratory criteria for pDILI for at least 1 visit and reporting at least 1 symptom potentially associated with hepatitis or hypersensitivity according to the Investigator on the pDILI CRF will be presented.

In addition, a table will be produced to summarize potential Hy's Law cases. The following two definitions will be used in that table (all criteria must be met at the same assessment):

- [AST \geq 3xULN or ALT \geq 3xULN] and Total Bilirubin \geq 2xULN in the absence of ALP \geq 2xULN

In case any study participants meeting the potential Hy's Law criteria, a plot displaying time course for serum LFTs will be provided on the AMS.

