Ab=antibody; ADE=adverse device effect; AE=adverse event; BKZ=bimekizumab; BSA=body surface area; CT=computed axial tomography; DLQI=Dermatology Life Quality Index; ECG=electrocardiogram; eCRF=electronic Case Report Form; HBcAb=anti-hepatitis B core antibody; HBsAg=hepatitis B surface antigen; HBV=hepatitis B virus; HCV=hepatitis C virus; HIV=human immunodeficiency virus; IGA=Investigator's Global Assessment; IGRA=interferon-gamma release assay; IMP=investigational medicinal product; IRT=interactive response technology; P-SIM=Psoriasis Symptom and Impact Measure; PASI=Psoriasis Area and Severity Index; PEOT=Premature End of Treatment; PSD=Patient Symptom Diary; Q4W=every 4 weeks; Q8W=every 8 weeks; scalp IGA=scalp-specific IGA; SFU=Safety Follow-Up; TB=tuberculosis

Note: All assessments should be performed prior to IMP administration. The IMP administration is the starting point for the next administration period. Thus, the assessments in Week 16 and Week 32 belong to the previous treatment period.

^a For visits from the first dose of IMP through Week 32, the visit window is ± 4 days from the scheduled visit. For the SFU Visit, the visit window is ± 7 days from the scheduled visit.

^b The SFU Visit will occur 17 weeks after the final dose of IMP.

^c Ensure no significant changes in medical history.

^d Includes evaluation of signs and symptoms of active TB and risk for exposure to TB.

^e The physical examination will be performed as described in Section 8.2.3.

^f Vital signs (sitting systolic and diastolic blood pressure, pulse rate, and body temperature) are to be measured prior to blood sampling and prior to dosing, where applicable.

^g Pregnancy testing will consist of serum testing at Screening. A urine pregnancy test will be administered at all other visits.

^h Study participants who have evidence of or test positive for hepatitis B or C are excluded from the study, per Exclusion Criterion #9 (Section 5.2). A positive test for HBV is defined as: 1) positive for HBsAg or 2) positive for HBcAb. A positive test for HCV is defined as: 1) positive for anti-HCV Ab and 2) positive via a confirmatory test for HCV (eg, HCV polymerase chain reaction).

ⁱ The HIV test results will not be recorded in the eCRF.

^j Screening chest x-ray/CT scan must occur within 3 months prior to Screening Visit.

Table 1-1: Schedule of Activities

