4.1.4 Treatment assignment and treatment groups

It is expected that study participants receive treatment as randomized for the ITP, or as assigned per protocol study design (via reallocation) for the MTP.

Safety analyses will be based on the SS, as randomized. However, if after unblinding it is determined that study participants randomized to placebo received bimekizumab at any time within the first 16 weeks, then for safety analyses these study participants will be reallocated to the appropriate bimekizumab treatment group, unless otherwise specified. Study participants randomized to bimekizumab will only be reallocated to the placebo treatment group if they never received bimekizumab.

Unless otherwise stated, the summary tables of safety analyses will be provided as:

- The ITP data will be displayed by Placebo and BZK 320mg Q4W columns based on the SS
- The MTP data will be displayed by BKZ 320mg Q4W and BKZ 320mg Q8W columns based on the MS by treatment received at the MTP
- The initial and maintenance treatment period data will be displayed by BKZ 320mg Q4W, BKZ 320mg Q8W, and BKZ 320mg Total columns based on the AMS

Study participants randomized to BKZ 320mg Q4W and received BKZ 320mg Q8W in the MTP will be represented in both the BKZ 320mg Q4W and BKZ 320mg Q8W treatment columns. BKZ 320mg Q8W column only presents the data after the switch from BZK 320mg Q4W to BKZ 320mg Q8W. BKZ 320mg Q4W column will also include study participants that switch from Placebo to BKZ 320mg Q4W (only data after switch).

Efficacy analyses should be performed according to randomized treatment and not actual treatment received.

Unless otherwise stated, the summary tables of efficacy analyses will be provided as:

- The ITP data will be displayed by Placebo and BZK 320mg Q4W columns based on the RS
- The MTP data will be displayed by BKZ 320mg Q4W column and BKZ 320mg Q8W column based on the MS by treatment received at the MTP
- The initial and maintenance treatment period data will be displayed by Placebo/BKZ 320mg Q4W and BZK 320mg Q4W/Q8W columns based on the randomized treatment sequence by RS

For all TFLs for demographics, baseline disease characteristics, previous and ongoing medical history, prior and concomitant medications, and psoriasis treatment history, the summary will be displayed by Placebo/BKZ 320mg Q4W and BKZ 320mg Q4W/Q8W columns based on the randomized treatment sequence.

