4.5.1.2 Exposure during the MTP

Definitions for study medication duration (days) and time at risk (days) during the MTP are provided as follows:

Study medication duration (days)

$$\text{Date of last active dose in the MTP} - \text{date of first dose in the MTP} + 28$$

The use of 28 days assumes a Q4W dosing interval. This will be adjusted based on the dosing interval (eg, for Q8W use Date of last active dose in the MTP – date of first dose in the MTP + 56 days).

- If the date of last active dose in the MTP + 28 days (or 56 days in the case of Q8W dosing) extends to a date beyond the date of last visit in the MTP (including PEOT, not including SFU), then this calculation reverts to:

$$\text{Date of last visit in the MTP} - \text{date of first dose in the MTP} + 1$$

- For study participants who died during the MTP, if date of last active dose in the MTP + 28 days (or 56 days in the case of Q8W dosing) extends beyond the date of death, then this calculation reverts to:

$$\text{Date of death} - \text{date of first dose in the MTP} + 1$$

Time at risk (days)

For study participants who died during the MTP:

$$\text{Date of death} - \text{date of first dose in the MTP} + 1$$

For study participants who complete the MTP (not including SFU) as scheduled or who discontinue the MTP early, use the minimum of the following:

- $\text{Date of last dose in the MTP} - \text{Date of first dose in the MTP} + 119$
- $\text{Date of last clinical contact} - \text{date of first dose in the MTP} + 1$

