4.5.1.3 Exposure during the Initial and Maintenance Treatment Period (combined)

Definitions for study medication duration (days) and time at risk (days) during the Initial and Maintenance Treatment Period (combined) are provided as follows:

Study medication duration (days)

Study medication duration will be summarized for BKZ 320mg Q4W, BKZ 320mg Q8W, and BKZ 320mg Total respectively:

- For BKZ 320mg Q4W:

Include study medication duration in ITP for study participants who are randomized to BKZ 320mg Q4W in ITP (refer to section 4.5.1.1 – study medication duration) and study medication duration in MTP for study participants who are randomized to placebo in ITP and switch to BKZ 320mg Q4W in MTP (refer to section 4.5.1.2 – study medication duration)

- For BKZ 320mg Q8W:

Include study medication duration in MTP for study participants who switch to BKZ 320mg Q8W in MTP (refer to section 4.5.1.2 – study medication duration)

- For BKZ 320mg Total:

For study participants randomized to BKZ 320mg Q4W in the ITP:

$\text{Date of last active dose} - \text{date of first dose in the ITP} + 28$ (if last active dose was in the ITP) or 56 (if last active dose was in the MTP)

- If the date of last active dose + 28 days (if last active dose was in the ITP) or 56 days (if last active dose was in the MTP) extends to a date beyond the date of last visit (including PEOT, not including SFU), then this calculation reverts to:

$\text{Date of last visit} - \text{date of first dose in the ITP} + 1$

- For study participants who died, if date of last active dose + 28 days (if last active dose was in the ITP) or 56 days (if last active dose was in the MTP) extends beyond the date of death, then this calculation reverts to:

$\text{Date of death} - \text{date of first dose in the ITP} + 1$

For study participants randomized to Placebo in ITP and switch to BKZ 320mg Q4W in MTP:

Include study medication duration in MTP defined in section 4.5.1.2 – study medication duration.

Time at risk (days)

Time at risk will be summarized for BKZ 320mg Q4W, BKZ 320mg Q8W, and BKZ 320mg Total respectively:

- For BKZ 320mg Q4W:

For study participants who are randomized to BKZ 320mg Q4W in ITP:

- For study participants who complete the final visit of the ITP (Week 16 visit) and continue to the MTP

Date of first dose in the MTP – date of first dose in the ITP + 1

- For study participants who died during the ITP

Date of death – date of first dose in the ITP + 1

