- For study participants who discontinue the ITP early or who complete the ITP but do not continue to the MTP, use the minimum of the following:

Date of last dose in the ITP – Date of first dose in the ITP + 119

Date of last clinical contact – date of first dose in the ITP + 1

For study participants who are randomized to placebo in ITP and switch to BKZ 320mg Q4W in MTP:

Include time at risk in MTP defined in section 4.5.1.2 – time at risk.

- For BKZ 320mg Q8W:

Include time at risk in MTP for study participants who switch to BKZ 320mg Q8W in MTP (refer to section 4.5.1.2 – time at risk).

- For BKZ 320mg Total:

For study participants randomized to BKZ 320mg Q4W in ITP:

- For study participants who died before the final visit (not including SFU):

Date of death – date of first dose in the ITP + 1

- For all the other study participants including who discontinue early or who complete the MTP as scheduled, use the minimum of the following:

Date of last dose – Date of first dose in the ITP + 119

Date of last clinical contact – date of first dose in the ITP + 1

For study participants who are randomized to Placebo in ITP and switch to BKZ 320mg Q4W in MTP:

Include time at risk in MTP defined in section 4.5.1.2 – time at risk

A by-study participant listing of exposure to study medications will be provided on the SS by treatment group.

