4.5.2 Adverse events

An AE is any untoward medical occurrence in a study participant or clinical investigation study participant administered a pharmaceutical product that does not necessarily have a causal

relationship with this treatment. An AE can therefore be any unfavorable and unintended sign (including an abnormal laboratory finding), symptom, or disease temporally associated with the use of a medicinal (investigational) product, whether or not related to the medicinal (investigational) product.

AEs will be coded according to the Medical Dictionary for Regulatory Activities (MedDRA version 19.0). All summaries will be provided by treatment group. The treatment group for each study participant will be defined as the treatment received at the onset of the AE. For study participants who switch treatment (ie, from placebo to bimekizumab or from bimekizumab Q4W to Q8W) at Week 16, any AEs that occur after initiation of the new treatment are attributable to the new treatment.

If an AE occurs on the date of a treatment switch, the event is attributed to the original treatment. The only exceptions are for the following types of events, which will be attributed to the new study treatment:

- Events that fulfill the anaphylaxis criteria for acute events (refer to Section 6.12)
- Events that fulfill the hypersensitivity reaction criteria (Hypersensitivity events will be identified using the “Hypersensitivity (Standardized MedDRA Query ([SMQ])”. All TEAEs which code to a Preferred Term (PT) included in the Scope=Narrow search will be included.)
- Events with a High Level Term (HLT) of “Administration site reactions NEC”
- Events with an HLT of “Injection site reactions”

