4.5.3.2 Vital signs

The following vital signs variables should be summarized: systolic blood pressure (mmHg), diastolic blood pressure (mmHg), body temperature (°C) and heart rate (beats/min). The following analyses will be provided:

For summaries for the ITP and Initial and Maintenance Period (combined) where multiple measurements across different visits are considered (as of markedly abnormal values tables), the vital sign results will be attributed according to their collection date and time at risk for each period (see Section 4.5.1).

- A summary of the absolute and change from Baseline value for each vital sign variable by treatment group and visit for the SS displaying the Placebo/BKZ 320mg Q4W and BKZ 320mg Q4W/Q8W.

- A summary of the number and percentage of study participants experiencing at least one markedly abnormal value for a vital sign variable as defined in Section 6.10.2, by treatment group. Two separate tables will show results for the ITP (for the SS) and the initial and maintenance treatment period (combined) (for the AMS).
- A by-study participant listing of all vital signs data will be provided for the SS. This listing should be presented by treatment group and will include: center, study participant identifier, age, sex, race, weight, visit, vital sign variable and result.

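### Laboratory and vital-sign results have no switch-date rule: read literally, SAP 4.5.3.1 and 4.5.3.2 put a pre-dose Week 16 result in both the pre-switch and post-switch windows

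*SAP*

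**What the plan says.** SAP 4.5.3.1 covers the laboratory tables that draw on more than one visit (markedly abnormal values, worst CTCAE grade, shifts). It states that "the laboratory results will be attributed according to their sampling date and time at risk for each period", and points to Section 4.5.1. SAP 4.5.3.2 has the matching rule for markedly abnormal vital signs: "the vital sign results will be attributed according to their collection date and time at risk for each period". The SAP version history shows that Amendment 2 added both. They apply to the ITP table on the Safety Set and to the combined ITP and MTP table on the Active Medication Set.

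For participants who continue, SAP 4.5.1.1 and 4.5.1.3 give the pre-switch time at risk as "Date of first dose in the MTP – date of first dose in the ITP + 1". For the MTP, SAP 4.5.1.2 says "For study participants who complete the MTP (not including SFU) as scheduled or who discontinue the MTP early, use the minimum of the following", and both candidate formulas count from the date of the first MTP dose. For placebo participants who switch, SAP 4.5.1.3 says "Include time at risk in MTP defined in section 4.5.1.2 – time at risk".

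Other text places Week 16 before the switch:
- The note to the schedule in Protocol 1.3 has assessments done before dosing and adds: "Thus, the assessments in Week 16 and Week 32 belong to the previous treatment period".
- SAP 4.1.1.2 ends the ITP before the first MTP dose and opens the MTP at the day and time of that dose.
- SAP 4.1.4 limits the Q8W column to data after the switch, and says of the other column: "BKZ 320mg Q4W column will also include study participants that switch from Placebo to BKZ 320mg Q4W (only data after switch".

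For adverse events, SAP 4.5.2 has an explicit tie rule, with listed exceptions for acute reactions: "If an AE occurs on the date of a treatment switch, the event is attributed to the original treatment". Laboratory and vital-sign results have no such rule.

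**The concern.** The attribution rule works on dates, and the two windows it refers to share a date. The Week 16 blood sample and vital signs are normally taken on that date, before the injection. A program that follows 4.5.3.1 and 4.5.3.2 to the letter would therefore place one pre-dose result in two treatment columns.

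One abnormal value is enough to classify a participant in these tables. A low neutrophil count or raised transaminase found at Week 16 in a placebo participant, before any bimekizumab, could be shown under bimekizumab Q4W and Total. An abnormality at the end of Q4W dosing could appear again under Q8W.

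Two other parts of the SAP do not prevent this:
- The exclusion of Baseline values in 4.5.3.1 does not help, because SAP 4.1.2 ties Baseline to the first administration of any study medication. For switchers that is placebo, so Week 16 is post-Baseline.
- SAP 4.6.1.1 treats the same Week 16 pre-dose observation as the switchers' baseline, but only for pharmacokinetics.

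**Working it through.** **Inputs.** First dose on Day 1. Doses at Weeks 16 and 28, the latter being the last (Protocol Table 6-2). Safety follow-up (SFU) visit 17 weeks, or 119 days, after the last dose (Protocol 1.3). Planned arms of 90 and 30 (Protocol 4.1). Time-at-risk formulas from SAP 4.5.1. The participant is on schedule, and last clinical contact is the SFU visit.

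**1. The plan's own figure.** 16 × 7 = 112 days, the ITP length in SAP 4.5.1.1. It is reproduced.

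**2. Study days.**
- Week 16: 1 + 112 = Day 113
- Week 28: 1 + 28 × 7 = Day 197
- SFU: 197 + 119 = Day 316

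**3. Time at risk for a participant who continues.**
- ITP: 113 − 1 + 1 = 113 days, so Days 1 to 113.
- MTP: the smaller of 197 − 113 + 119 = 203 and 316 − 113 + 1 = 204. That is 203 days, so Days 113 to 315.
- Bimekizumab Total, bimekizumab arm: the smaller of 197 − 1 + 119 = 315 and 316 − 1 + 1 = 316. That is 315 days.

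**4. Overlap.** 113 + 203 = 316, against 315 for Total. One day, Day 113, is in both windows.

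**5. Scheduled results against the windows** (visits from the schedule in Protocol 1.3).

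| Visit | Day | Laboratory | Vital signs | ITP window | MTP window |
|---|---|---|---|---|---|
| Week 4 | 29 | yes | yes | yes | no |
| Week 16 | 113 | yes | yes | yes | yes |
| Week 20 | 141 | yes | yes | no | yes |
| Week 24 | 169 | yes | no | no | yes |
| Week 32 | 225 | yes | yes | no | yes |
| SFU | 316 | yes | yes | no | no |

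Week 16 is the only scheduled result in both windows.

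**6. Columns under the literal reading.**
- Bimekizumab arm (up to 90): Week 16 counts under both Q4W and Q8W in the combined table. In Total it counts once.
- Placebo arm (up to 30): Week 16 counts under Placebo in the ITP table, and under Q4W and Total in the combined table.

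**7. Upper limit of the effect.** The documents give no rate of markedly abnormal Week 16 values, so 0.5% to 5% of participants is assumed.
- Q4W column (about 90 + 30 = 120): 30 × 0.005 = 0.15 to 30 × 0.05 = 1.5 participants added. 0.15/120 = 0.125 and 1.5/120 = 1.25 percentage points.
- Q8W column (90): 90 × 0.005 = 0.45 to 90 × 0.05 = 4.5 participants added, which is 0.5 to 5 percentage points.

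These are ceilings. They assume that everyone continues and is sampled on the dose date, and a participant already counted in that column adds nothing.

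**8. With a same-day rule.** For pre-dose results the post-switch window opens on Day 114. The overlap falls from one day to none.

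**The case against.** The strongest reply is that the SAP already gives the right answer. SAP 4.1.1.2 separates the periods by day and time, SAP 4.1.4 governs the safety tables unless otherwise stated and admits only post-switch data, and the schedule note gives Week 16 to the earlier period. Time at risk in 4.5.1 is a day count for participant-years and exposure-adjusted rates, and the added day is ordinary inclusive counting. On this view nobody intended an overlap.

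Much of that stands. A reader might infer that the SAP prescribes double counting. It does not: nothing says that a result counts in two columns or that 4.5.3 overrides 4.1.4. The reply does not close the gap, however. The rule in 4.5.3.1 and 4.5.3.2 is the later and more specific text, it refers to 4.5.1 and not 4.1.1.2, and it uses the day count to place dated results. SAP 4.5.2.2 attributes adverse events by onset date and time at risk in the same way, and there 4.5.2 supplies a tie rule.

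Three broader readings also go too far:
- **That placebo-period abnormalities in general would count as bimekizumab.** Only a result dated on the first MTP dose date can move. The Week 4 result cannot.
- **That every Week 16 result or every table is affected.** By-visit tables use the randomized sequence. Participants who never start the MTP, or whose sample is on a different date from the first MTP dose, are not double-counted. Within-table duplication concerns only the bimekizumab arm.
- **That the effect can be stated as a share of each switcher's post-switch results.** The count is not settled. Protocol 1.3 and 8.2.2 differ on how often vital signs are taken, and an on-schedule SFU sample falls one day outside the 203-day window. A per-switcher figure would not be a column figure either.

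It is also fair to say that the tables are descriptive and that the listings show each result by visit, so any misplacement can be traced.

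**Conclusion.** The point holds as an internal contradiction with a missing tie rule. Followed literally, the attribution rule puts a pre-dose result from the first MTP dose date in both windows, contrary to Protocol 1.3 and SAP 4.1.1.2 and 4.1.4. Whether results would actually be misplaced depends on how the tables are programmed, which the documents do not show.

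The overlap of one day follows from the SAP's formulas for an on-schedule participant. The percentages do not: under the assumed 0.5% to 5%, they are at most 0.125 to 1.25 points in the Q4W column (the same ceiling applies to Total, also about 120 participants) and at most 0.5 to 5 points in the Q8W column. The worst-grade and shift tables also use lower grades, and no figure is offered for those.

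No efficacy result or hypothesis test is touched. The correction should still be made, because these tables describe laboratory and vital-sign safety by regimen and the remedy is small.

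**What to change.** Add to SAP 4.5.3.1 and 4.5.3.2:

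> Laboratory and vital-sign results (scheduled or unscheduled) collected on the date of the first MTP dose are attributed to the pre-switch treatment (ITP) only, unless the recorded collection time is after that dose; post-switch columns use only results collected after that dose.

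This follows the general switch-date convention for adverse events and brings the two sections into line with Protocol 1.3 and SAP 4.1.1.2 and 4.1.4. The cost is one sentence in each section and one programming condition. It needs no new data: where no collection time was recorded, the result stays with the pre-switch treatment.
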